3.2 Secondary Objective(s) & Hypothesis(es)

- 1) **Objective:** To evaluate the efficacy of co-administered MK-3682 (450 mg) + RZR (180 mg) as assessed by the proportion of subjects achieving SVR at 24 weeks post-treatment (SVR₂₄) (defined as HCV RNA <LLOQ 24 weeks after the end of all study therapy).
- 2) **Objective:** To evaluate the efficacy of co-administered MK-3682 (450 mg) + RZR (180 mg), as assessed by the proportion of subjects experiencing virologic failure (either on-treatment failure or relapse post-treatment) at Follow-up Week (FW) 12 among subjects who do not discontinue study for non-treatment-related (e.g., administrative) reasons.
- 3) **Objective:** To evaluate the effect of baseline resistance-associated variants (RAVs) in nonstructural protein (NS) 5A and/or NS5B on the efficacy of co-administered MK-3682 (450 mg) + RZR (180 mg), as assessed by the proportion of subjects with baseline RAVs achieving SVR₁₂.

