4.2.5.1.1 Measurement of HCV RNA

HCV-RNA levels in plasma will be measured using the Roche COBAS® AmpliPrep/COBAS® TaqMan® HCV Test, v2.0 on blood samples drawn from each subject at various time points prior to, during, and after dosing, as indicated in the Trial Flow Chart (Section 6.0). Samples are collected and processed as per instructions provided by the manufacturer.

Results from the sample collected at the screening visit are used to determine eligibility. Samples collected at other time points, after Day 1, are used for efficacy analyses and to identify subjects who meet virologic failure criteria.

The nomenclature detailed in Table 5 will be used when describing HCV RNA levels:

Table 5 Nomenclature for Describing HCV RNA Levels

Abbreviation	Definition	HCV RNA Level
TND	Target not detected	HCV RNA not detected
TD(u)	Target detected but unquantifiable	HCV RNA <LLOQ
TD(q)	Target detected, quantifiable	HCV RNA ≥LLOQ

HCV = hepatitis C virus; LLOQ = lower limit of quantification; RNA = ribonucleic acid.

4.2.5.1.1.1 Definition of Efficacy Endpoints

Efficacy will be defined at different time points during the trial. Specific primary and secondary endpoints are:

- SVR₁₂: Subject has HCV RNA <LLOQ 12 weeks after the end of all study therapy.
- SVR₂₄: Subject has HCV RNA <LLOQ 24 weeks after the end of all study therapy.
- Virologic failure rate among subjects who do not discontinue the study for non-treatment-related reasons at FW12.

4.2.5.1.1.2 Definition of Virologic Failure: Non-Response, Rebound, Virologic Breakthrough and Relapse

Lack of efficacy at different time points in the trial will be categorized as:

- Non-response: Subject has HCV RNA detected at end of treatment without HCV RNA <LLOQ having been achieved while on treatment (note that breakthrough is distinguished below).
- Rebound: Subject has a rebound defined as >1 log₁₀ IU/mL increase in HCV RNA from nadir while on treatment and confirmed from a separate blood draw within 2 weeks.

- **Virologic breakthrough:** Subject has a confirmed HCV RNA \geq LLOQ (target detected, quantifiable [TD(q)]) after being $<$ LLOQ previously while on treatment. Confirmation is defined as an HCV RNA \geq LLOQ from a separate blood draw repeated within 2 weeks.

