- **Relapse:** Subject has a confirmed HCV RNA \geq LLOQ [TD(q)] following end of all study therapy, after becoming undetectable (target not detected [TND]) at end of treatment. Confirmation is defined as an HCV RNA \geq LLOQ from a separate blood draw repeated within 2 weeks.

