8.4.1 Efficacy/Pharmacokinetics Endpoints

8.4.1.1 Efficacy Endpoints

An initial description of efficacy measures is provided in Section 4.2.5.1.

The primary efficacy endpoint is the proportion of subjects achieving SVR₁₂.

The secondary efficacy endpoints are the following:

1. The proportion of subjects achieving SVR₂₄;
2. The proportion of subjects experiencing virologic failure (either on-treatment failure or relapse post-treatment) through FW12 among all subjects who do not discontinue study for non-treatment-related reasons.

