8.5.1 Efficacy Analysis Populations

Full Analysis Set (FAS)

The FAS population will serve as the primary population of efficacy data in this study. The FAS population consists of all subjects who are assigned to treatment and receive at least 1 dose of study treatment in this study.

Per Protocol (PP)

The PP population will serve as a supportive analysis population. The PP population excludes subjects due to important deviations from the protocol that may substantially affect the results of the primary and secondary efficacy endpoints. Non-virologic failures that are due to administrative (non-treatment-related) reasons will be excluded. Potential violations that may result in the exclusion of a subject from the PP population also include the following:

- The subject did not meet specific inclusion/exclusion criteria (for example, the subject is infected with a mixed GT infection or non-typeable GT).
- The subject received concomitant medications that are prohibited due to their potential to result in a clinically significant lowering of the MK-3682 or RZR concentrations (see Section 5.5 for specific details of prohibited medications). Further, any co-administered medication currently unidentified, but for which subsequent clinical drug-drug interaction data indicate that co-administration with MKs leads to a clinically significant lowering of MK concentrations, may also exclude a subject from the per-protocol population..
- Other violations may be identified during the course of data collection and they will be listed specifically in the CSR.

A subject with important deviations from the protocol at treatment allocation (Day 1) will be excluded from the PP population. For subjects with important deviations from the protocol as described above during the course of treatment, data obtained subsequent to the violation will be excluded from analysis.

Modified Full Analysis Set (mFAS)

The mFAS population will be used for supportive analysis of the efficacy endpoints of SVR₁₂ and SVR₂₄ and as primary analysis for the endpoint of the proportion of subjects experiencing virologic failure at FW12 as a primary analysis. The mFAS population is a subset of the FAS population, with subjects excluded for study discontinuation for reasons unrelated to the treatment regimen. Examples include loss to follow-up, discontinuation from the study due to non-drug related AEs, informed consent withdrawal, and other non-virologic failures.

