8.6.1 Statistical Methods for Efficacy Analyses

Missing Values

A missing data point for a given study visit may be due to any one of the following reasons: a visit occurred but data were not collected or were unusable; a visit did not occur; or a subject discontinued from the study before reaching the visit. Subjects who prematurely discontinued the assigned treatment are encouraged to remain in the study for follow-up, if possible.

The HCV RNA outcome is categorized as TND, TD (u), and TD (q). There are 3 types of missing data handled by different approaches.

1. Intermittent missing: If a missing data point is immediately preceded and followed by non-missing HCV RNA outcomes, the missing value would be imputed to the worst outcome of the two. For example, if a missing data point is preceded by TD(q) and followed by TD(u) or TND, then the missing value would be imputed as TD(q); if a missing data point is preceded by TD(u) and followed by TND, then the missing value would be imputed as TD(u); when a missing value is flanked by two TND, then the missing value would be imputed as TND.
2. Non-intermittent missing related to the study drug: For missing values due to premature study discontinuations due to treatment-related reasons either for safety or efficacy, the missing values will be considered as treatment failures.
3. Non-intermittent missing for reasons unrelated to the study drug: For missing data due to premature study discontinuations with reasons unrelated to treatment such as loss to follow-up, protocol deviation, withdrawal of consent, administrative reasons, etc., the missingness mechanism is unlikely to be related to subjects' response to the HCV treatment, and therefore the missing at random assumption is reasonable.

The following 2 approaches will be used to handle non-intermittent missing data due to premature discontinuations, depending on the analytical strategy, as described in the section below and in [Table 15](#).

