1. Treatment-Related Discontinuation=Failure (TRD=F) approach: Subjects with treatment-related missing data (type #2 above) will be considered as failure; whereas the subjects who have the non-treatment-related missing value (type #3 above) and who do not have virologic failure during the observed study period will be excluded from the analysis for the time points following their study withdrawal. Note that subjects with documented virologic failure during the treatment or follow-up period, even if they withdrew prematurely due to reasons not related to study drug, are classified as failures.
2. Missing=Failure (M=F) approach: Subjects with any non-intermittent missing data (i.e., type #2 and #3 above) will be imputed as failures, regardless of the reason for study discontinuation.

In addition, a missing baseline/Day 1 HCV RNA result will be replaced with a screening result, if available.

Proportions of Subjects With Virologic Responses and Virologic Failures

For the primary efficacy analysis, the proportions of subjects achieving SVR₁₂ for each GT will be provided and 95% CIs for these rates will be calculated using the Clopper-Pearson method [42]. The same method will be used to analyze all binary endpoints including SVR₄, SVR₈, SVR₂₄, and virologic response rates at TW4, TW8, and end of treatment.

For the primary analyses using the FAS population, the M=F missing data approach will be utilized. In these analyses, only subjects with HCV RNA levels <LLOQ for any type of HCV infection at a given time point will be considered to have achieved the endpoint.

For all analyses conducted using the PP and mFAS populations, the missing data approach of TRD=F will be utilized. In addition, for all analyses based on these 2 populations, a subject will be considered to have achieved a response for a particular endpoint if the HCV RNA levels for the infection he/she had at baseline are <LLOQ. For example, if a subject has HCV RNA levels \geq LLOQ at a particular time point, but those RNA levels correspond to an infection that is of a different GT and/or subtype compared to the infection detected at baseline and the baseline infection has been cleared, then the subject is considered to have achieved response for the given endpoint.

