To estimate the secondary efficacy endpoint of proportion of subjects experiencing virologic failure at FW12 for each GT, 95% CIs for these rates will be calculated in the mFAS analysis population using the Clopper-Pearson method [42]. The missing data approach of TRD=F described previously will be utilized for this analysis.

[Table 15](#) includes a summary of the key efficacy analyses, and [Table 16](#) includes a summary of the analysis populations and various criteria to assess the primary endpoint (SVR₁₂) and secondary endpoints (SVR₂₄ and proportion of subjects experiencing virologic failure at FW12).

Table 15 Analysis Strategy for Efficacy Variables

Endpoint/Variable (Description, Time Point)	Primary vs. Supportive Approach	Statistical Method	Analysis Population	Missing Data Approach
Primary				
Proportion of subjects achieving SVR ₁₂ by genotype	P	95% CI (Clopper-Pearson)	FAS	M=F
Proportion of subjects achieving SVR ₁₂ by genotype	S	95% CI (Clopper-Pearson)	mFAS	TRD=F
Proportion of subjects achieving SVR ₁₂ by genotype	S	95% CI (Clopper-Pearson)	PP	TRD=F
Secondary				
Proportion of subjects achieving SVR ₂₄ by genotype	P	95% CI (Clopper-Pearson)	FAS	M=F
Proportion of subjects achieving SVR ₂₄ by genotype	S	95% CI (Clopper-Pearson)	mFAS	TRD=F
Proportion of subjects achieving SVR ₂₄ by genotype	S	95% CI (Clopper-Pearson)	PP	TRD=F
Proportion of subjects experiencing virologic failure at FW12 by genotype	P	95% CI (Clopper-Pearson)	mFAS	TRD=F
CI = confidence interval; FAS = Full Analysis Set; M=F = Missing=Failure; mFAS = modified Full Analysis Set; P = primary approach; PP = Per Protocol; S = secondary approach; TRD=F = Treatment-Related Discontinuation=Failure.				

Table 16 Analysis Populations, Criteria for Response, Non-Response, and Exclusion from Analysis Populations

Analysis Population	Criteria for Response	Criteria for Non-Response	Criteria for exclusion from analysis population
FAS (Primary for SVR ₁₂ and SVR ₂₄)	HCV RNA < LLOQ	HCV RNA ≥ LLOQ	Subject did not receive at least 1 dose of study medication

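### TRD=F, applied to virologic failure at FW12, would count a subject who leaves the study for a drug-related reason with suppressed virus as a virologic failure

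*Combined protocol and SAP*

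**What the plan says.** Section 8.4.1.1 defines the endpoint as "The proportion of subjects experiencing virologic failure (either on-treatment failure or relapse post-treatment) through FW12", among subjects who do not leave the study for non-treatment-related reasons. Section 3.2 states the objective in the same terms. Section 4.2.5.1.1.2 gives four categories: non-response, rebound, breakthrough and relapse. All rest on HCV RNA, and the last three need a confirmatory blood draw. Relapse means confirmed quantifiable virus "following end of all study therapy, after becoming undetectable (target not detected [TND]) at end of treatment".

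Section 8.6.1 and the last row of Table 15 analyse this endpoint in the mFAS with TRD=F: "The missing data approach of TRD=F described previously will be utilized for this analysis". Section 8.6.1 describes the relevant missing data as arising from study discontinuation "due to treatment-related reasons either for safety or efficacy, the missing values will be considered as treatment failures". The rule itself reads: "Subjects with treatment-related missing data (type #2 above) will be considered as failure". It does not refer to the last HCV RNA result and makes no exception for this endpoint. A further sentence in Section 8.6.1, repeated in the Section 8.1 summary, applies TRD=F to PP and mFAS analyses generally.

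The mFAS is the FAS "with subjects excluded for study discontinuation for reasons unrelated to the treatment regimen" (Section 8.5.1), so subjects who leave for drug-related reasons stay in the denominator.

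**The concern.** TRD=F was built for a response endpoint. For SVR12, a subject driven off study by the drug has not been shown to respond, and failure is a sensible label. The virologic-failure endpoint has only one failure state, which is virologic failure. Carried over unchanged, the rule records a virologic event for someone whose virus was below LLOQ when last measured and who meets none of the four categories.

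At stake is what the secondary estimate and its confidence interval mean. Table 18 illustrates between 0 and 3 non-responders per group, so one reclassified subject is a visible share of the count. The estimate could also disagree with the rates of non-response, rebound, breakthrough and relapse that Section 8.6.1 plans to report alongside it.

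**Working it through.** **Inputs from the documents.** Genotype sizes are 50 for GT1 to GT4 (GT1 being 35 GT1a plus 15 GT1b) and 25 for GT5 and GT6 (Section 8.9.1). Intervals are two-sided 95% Clopper-Pearson.

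**Assumed inputs.** V is the number of subjects meeting a Section 4.2.5.1.1.2 category. K is the number who leave the study for a drug-related reason with suppressed virus and no later HCV RNA. The plan gives no expected value for either.

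**Reproducing the plan's figures.** Exact intervals from beta quantiles return all 16 rows of Table 18, for example 49/50 = 98.0% (89.4, 99.9) and 24/25 = 96.0% (79.6, 99.9). The plan prints no figure for virologic failure.

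**Effect of the rule.** As written, the estimate is (V + K)/n. Counting virologic events only, it is V/n. The difference is K/n, which for each such subject is 1/50 = 2.0 points or 1/25 = 4.0 points.

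| n | V | K | As written, (V+K)/n | Virologic events only, V/n | Those K excluded, V/(n−K) |
|---|---|---|---|---|---|
| 50 | 1 | 0 | 2.0% (0.1, 10.6) | 2.0% (0.1, 10.6) | 2.0% (0.1, 10.6) |
| 50 | 1 | 1 | 4.0% (0.5, 13.7) | 2.0% (0.1, 10.6) | 2.0% (0.1, 10.9) |
| 50 | 2 | 2 | 8.0% (2.2, 19.2) | 4.0% (0.5, 13.7) | 4.2% (0.5, 14.3) |
| 25 | 1 | 1 | 8.0% (1.0, 26.0) | 4.0% (0.1, 20.4) | 4.2% (0.1, 21.1) |

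With K = 0 there is no inflation.

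**Relation to SVR12.** The supportive SVR12 analysis uses the same population and the same rule. With n = 50, V = 2 and K = 2 it is 46/50 = 92.0%, and 100 − 92.0 = 8.0%, the as-written failure rate. The primary SVR12 uses the FAS with M=F and does not match. Take a FAS of 50 with V = 1, K = 1 and 4 dropouts for non-treatment-related reasons:

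- one minus primary SVR12 = (1 + 1 + 4)/50 = 12.0%
- mFAS failure rate as written = (1 + 1)/(50 − 4) = 2/46 = 4.3%
- virologic events only = 1/46 = 2.2%

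**Can such a subject arise?** Section 5.8.1 says that stopping treatment is not leaving the trial, and the drug-related safety rows of Table 11 keep subjects under observation. The first row of Table 11 does remove a subject from treatment and trial when a medical condition creates unnecessary risk, and Section 5.8.2 allows withdrawal at any time. Suppression comes early: in PN021, on a three-drug regimen, 85/92 had HCV RNA below 15 IU/mL at Treatment Week 4. In Part A of PN011/PN012 none of 240 subjects discontinued for an adverse event. The exact 95% upper bound is 1 − 0.025^(1/240) = 1.5%, or 0.015 × 50 ≈ 0.8 subjects per genotype of 50. In Part C one of 24 subjects withdrew with drug-related events on a ribavirin-containing regimen, but after a single dose and with no HCV RNA result reported. That shows a way out of the study, not a suppressed subject.

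**The case against.** The strongest reply is that the trigger is narrow. TRD=F acts on study discontinuation, and most subjects who stop drug for an adverse event remain in follow-up and can have an observed FW12 result. This stands. A reader might infer that every drug-related treatment stop becomes a virologic failure; Sections 5.8.1 and 7.1.5.6 do not support that.

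Second, a reader might infer that the endpoint becomes one minus SVR12 and adds nothing. That goes too far. The match is with the supportive mFAS SVR12 only, and it is approximate: three of the four categories need confirmation, relapse requires target not detected at end of treatment, and events count through FW12. With no such dropouts the two are near complements under either rule, so TRD=F is not the main reason for the closeness.

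Third, the rule says failure or treatment failure, and Section 8.6.1 uses virologic failure as a separate term, so the text may lack a clarification rather than order a relabelling. That reading is fair, but it leaves these subjects with no rule for this endpoint, and the sentence still needs correcting.

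Fourth, the true events can be recovered from the planned rates by category, and Table 17 reports discontinuation due to adverse events. This limits the harm to the secondary estimate and its interval. It does not make that estimate match its definition.

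Fifth, calling these subjects non-events assumes no later relapse and so favours the drug. This is correct, and the fix has to allow for it. The objective also deliberately keeps treatment-related discontinuations in the denominator, and the fix respects that.

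**Conclusion.** The point holds in limited form. Followed as written, the plan counts as a virologic failure a subject who leaves the study for a drug-related reason, with suppressed virus and no later HCV RNA, although the endpoint's own definition would not. The size is 2 points per subject at n = 50 and 4 points at n = 25. It rests wholly on the assumed number of such subjects, which may be zero; the Part A experience comes from different regimens and is context only.

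A reader might infer that the stopping decisions are contaminated. They are not: Section 5.11.4 names the virologic categories directly and does not depend on TRD=F. The primary SVR12 analysis is also untouched, and the trial tests no hypothesis. The correction should be made before database lock because the rule and the definition conflict and the repair is cheap, not because a large bias is expected.

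**What to change.** 1. In the Section 8.6.1 sentence on virologic failure at FW12, and in its Table 15 row, replace TRD=F with a rule that counts as events only subjects meeting a Section 4.2.5.1.1.2 category.
2. Add an exception for this endpoint to the Section 8.6.1 sentence that applies TRD=F to all PP and mFAS analyses, and carry it into the Section 8.1 summary. Otherwise the conflict remains.
3. Keep treatment-related study discontinuations without documented virologic failure in the mFAS denominator as non-events, and tabulate them by genotype as non-virologic, treatment-related failures.
4. Report beside the main estimate a sensitivity analysis that excludes those subjects, since counting them as non-events assumes they would not have relapsed.
5. Retain TRD=F for SVR12 and SVR24 in the mFAS and PP populations.

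The cost is a few lines of text, one table cell and one added sensitivity display. No new data are needed, and Section 8.0 allows the change to be documented in the supplemental SAP before final database lock.

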8.6.2 Statistical Methods for Safety Analyses

Safety and tolerability will be assessed by clinical review of all relevant parameters including AEs and laboratory parameters. The 95% CIs for the safety parameters will be estimated

using the Clopper-Pearson method [42], which is a conservative exact method of providing CIs in this estimation study.

The analysis of safety parameters will follow a tiered approach (Table 17). The tiers differ with respect to the analyses that will be performed.

The first tier includes (1) AEs of elevated laboratory values that are reported as ECIs described in Section 7.2.3.2; (2) at least 1 AE; (3) a drug-related AE; (4) an SAE; (5) a serious and drug-related AE, and (6) an AE leading to discontinuation. Point estimates and 95% CIs will be provided.

The second tier includes specific AEs by SOC, vital signs, 12-lead ECGs, and standard laboratory safety tests at time points specified in the Trial Flow Chart (Section 6.0). Point estimates will be provided.

Missing safety laboratory, vital signs, or ECG values will be handled using the Data-As-Observed approach, that is, any missing value will be excluded from the analysis. The only exception is when a Baseline/Day 1 result is missing, this will be replaced with the latest pre-treatment result, if available.

Missing safety laboratory, vital signs, or ECG values will be handled using the Data-As-Observed approach, that is, any missing value will be excluded from the analysis. The only exception is when a Baseline/Day 1 result is missing, this will be replaced with the latest pre-treatment result, if available.

The primary safety analysis will summarize the safety data for subjects during the treatment period plus 14 days of follow-up.

Table 17 Analysis Strategy for Safety Parameters

Safety Endpoint ¹	95% CI	Descriptive Statistics
AEs of elevated laboratory values that are reported as ECIs	X	X
Any AE	X	X
Any SAE	X	X
Any Drug-Related AE	X	X
Any Serious and Drug-Related AE	X	X
Discontinuation due to AE	X	X
Specific AEs, SOCs or PDLCS		X
Change from Baseline Results (laboratory, vital signs, ECG)		X

AE = adverse event; ECG = electrocardiogram; ECI = event of clinical importance; n/a = not applicable; PDLC = pre-defined limit of change; SOC = system organ class; X = results will be provided.

¹ Adverse Experience references refer to both Clinical and Laboratory AEs.

